3.9. Data analysis

Analysis populations:

Two analysis populations will be defined:

- Enrolled Population (EP) - All patients for whom written informed consent has been obtained
- Safety Population (SP) - All patients in the EP who received at least one dose of belantamab mafodotin. The SP will be used for descriptive, safety and effectiveness analyses

Statistical Methods:

For the primary objective, characteristics of RRMM patients treated with belantamab mafodotin per routine clinical care will be described for the SP (overall and by line of treatment). Characteristics to be described include demographics, disease status, clinical characteristics and treatment history collected before or at the time of the first dose.

For the secondary objectives, the following will be described for the SP (overall and by line of treatment):

- Treatment dose, duration, persistence and adherence
- Ocular AESIs during the study period:
- Number, proportions, co-occurrence, time to (specific) ocular AESIs and incidence rate (at the patient and event level); overall and by System Organ Class (SOC) and Preferred Term (PT) terms (Medical Dictionary for Regulatory Activities [MedDRA] classification) and according to severity, grade, seriousness, action taken, duration, impact on daily living and relationship to treatment as well as treatment dose and frequency

- Number, proportion, severity, grade, seriousness and duration of ocular AESIs by ophthalmic monitoring frequency, type(s) and timing relative to administration
- Severity, grade, seriousness and duration of ocular AESIs by their treatment impact (e.g., dose changes, duration of interruptions/delays, discontinuation), use of artificial tears and dry eye comorbidity
- Number and proportions of patients with dose reductions, interruptions/delays or discontinuing treatment due to an ocular AESI during the study period: overall and by comorbidity. This will include the description of the timing and dose of treatment re-introductions and the duration of dose reductions and interruptions/delays
- Treatment response (e.g., complete response [CR], very good partial response [VGPR]; partial response [PR]; according to IMWG criteria if feasible or to local standard practice) and time to events (i.e., death, progression, discontinuation)

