Continuous variables will be described (distribution) by their mean, standard deviation, median, first and third quartile (Q1 and Q3), extreme values (minimum and maximum) and the number of non-missing and missing data. Categorical variables will be described using frequency counts and percentages.

Data analysis:

The following measures will be reported:

- Exposure-adjusted incidence and event rates with 95% confidence intervals of ocular AESIs (i.e., at the patient level and the event level): overall and by SOC and PT terms (MedDRA classification).
- Median, 95% confidence intervals (CIs) and 25th and 75th percentiles using the Kaplan-Meier (KM) method for time to event outcomes (i.e., OS, rwPFS, DoR, time to discontinuation, time to first [specific] ocular AESI)
- OS rates with 95% CIs at specified time points, including 12- and 15-months of follow-up
- Overall response rate (ORR) with 95% CIs calculated based on the exact binomial distribution (Clopper-Pearson method).

Additional subgroup analyses will be conducted for primary and secondary outcomes by key patient characteristics (e.g., Eastern Cooperative Oncology Group [ECOG] performance status, age groups at the index date, MM subtype, retrospective vs prospective data, and presence or absence of ocular AESIs) when deemed applicable and feasible, as described in the Statistical Analysis Plan (SAP).

Details of interim analyses will be described in the SAP.

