Belantamab mafodotin (BLENREP™) is a first in-class anti-B-cell maturation antigen therapy approved for use in the United States (US) and European Union (EU) based on data from the pivotal Phase II DREAMM-2 study (Study 205678) (Lonial, 2020; Lonial, 2021a). DREAMM-2 is a phase II, open label, randomized, two-arm study investigating the efficacy and safety of two doses of belantamab mafodotin (3.4 mg/kg vs. 2.5 mg/kg) in participants with MM who had ≥ 3 prior lines of treatment, were refractory to a proteasome inhibitor and an immunomodulatory agent and had failed an anti-CD38 antibody (Lonial, 2020; Lonial, 2021a). DREAMM-2 results after 13-month follow-up showed an overall response rate (ORR) for the 97 patients who received the registration dose (i.e., 2.5 mg/kg) of 32% (97.5% confidence interval [CI], 21.7-43.6) with 58% of responders achieving a very good partial response (VGPR) or better, including 2 stringent complete responses (sCRs) and 5 CRs (Lonial, 2021a). Median estimated duration of response (DoR), OS, and progression-free survival (PFS) were 11.0 months (95% CI, 4.2 months to not reached), 13.7 months (95% CI, 9.9 months to not reached), and 2.8 months (95% CI, 1.6-3.6 months), respectively (Lonial, 2021a). The most frequent adverse reactions ($\geq 30\%$) reported from 95 patients in DREAMM-2 who received belantamab mafodotin 2.5 mg/kg were keratopathy (71%) and thrombocytopenia (38%). The most commonly reported serious adverse reactions were pneumonia (7%), pyrexia (7%) and infusion-related reactions (3%). Permanent discontinuation due to an adverse reaction occurred in 9% of patients who received belantamab mafodotin with 3% related to ocular adverse reactions.

In the EU, belantamab mafodotin was granted a Conditional Marketing Authorisation on 25 August 2020 for the treatment of MM in adult patients who have received at least four prior therapies and whose disease is refractory to at least one PI, one immunomodulatory agent, and an anti-CD38 mAb, and who have demonstrated disease progression on the last therapy. Because of the risk of ocular toxicity, the European Medicines Agency (EMA) required additional monitoring and additional risk minimisation measures in the

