8.7.2.4. Analysis of Other Secondary Objectives

In addition, the following will be described for the SP (overall and by line of treatment):

- Exposure-adjusted incidence rate with 95% CI, overall and by SOC and PT names
 - Defined as the number of patients with at least one (specific) AE during follow-up divided by the sum of person-months at risk in the study.
 - Person-months at risk is defined as the duration of follow-up for patients without AEs plus the duration of follow-up until the date of the first (specific) AE for patients with an AE.
- Exposure-adjusted event rate with 95% CI, overall and by SOC and PT names
 - Defined as the number of (specific) AESIs during follow-up divided by the sum of person-months at risk in the study.
 - Person-months at risk is defined as the duration of follow-up.
- For patients with dose reductions, interruptions/delays or discontinuation of belantamab mafodotin treatment **due to an ocular AESI** during the study period, the following will be summarized (overall and by comorbidity, ocular AESI type and ocular AESI severity as well as treatment dose and frequency):
 - Number and proportions of patients
 - Primary reasons for dose reductions, interruptions/delays or discontinuation of treatment due to any AE
 - Belantamab mafodotin treatment patterns after occurrence of an ocular AESI (i.e., order of treatment changes and timing)

- Median, 95% CIs and 25th and 75th percentiles using the Kaplan-Meier (KM) method for time to dose reductions, interruptions/delays or discontinuation
- Duration of dose reductions and interruptions/delays or discontinuations
- Belantamab mafodotin treatment adherence, i.e., the total duration of treatment in days divided by the total follow-up time in days.
- Belantamab mafodotin treatment persistence, i.e., the proportion of patients still on treatment at specified time points, including 3-, 6-, 12- and 15-months of follow-up
- Treatment response (e.g., sCR, CR, VGPR or PR):
 - Best treatment response during follow-up
 - Treatment response at specified time points, including 12- and 15-months of follow-up
 - Proportion of patients with a maintained response (PR or better) at specific time points, including 12- and 15-months of follow-up
 - ORR with 95% CIs calculated based on the exact binomial distribution (Clopper-Pearson method)
- Median, 95% CIs and 25th and 75th percentiles using the KM method for:
 - OS (overall and based on response / non-response to treatment)

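### KM time to an ocular-AESI-driven treatment change seems confined to patients who had the change; name the Safety Population as risk set and use cumulative incidence

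*Protocol*

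**What the plan says.** Protocol 8.7.2.4 describes its analyses for the SP. One item then opens with "For patients with dose reductions, interruptions/delays or discontinuation of belantamab mafodotin treatment" and limits this to changes caused by an ocular AESI. The list that follows starts with "Number and proportions of patients", then gives reasons and treatment patterns. Next come "Median, 95% CIs and 25th and 75th percentiles using the Kaplan-Meier (KM) method for time to dose reductions, interruptions/delays or discontinuation" and an item on the duration of the changes. The KM item names no risk set, cause, time origin or censoring rule.

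Protocol 3.9 lists "Number and proportions of patients with dose reductions, interruptions/delays or discontinuing treatment due to an ocular AESI during the study period" for the SP and places the duration of reductions and interruptions inside that same item. Its KM outcomes include "time to discontinuation, time to first [specific] ocular AESI"; time to an ocular-AESI-driven change is not among them.

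For scale, 6.1 reports from the pivotal phase II study that permanent discontinuation due to an adverse reaction occurred in "9% of patients who received belantamab mafodotin with 3% related to ocular adverse reactions".

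**The concern.** One of the other secondary objectives is the impact of ocular AESIs on discontinuation, interruption/delay and dose modification. A time-to-event analysis serves that objective only if it starts with everyone exposed and shows how many are affected by when. If the KM item covers only patients who had the change, it answers a narrower question: among those affected, when did it happen? A short median could then be quoted as if it measured burden, although it would look much the same whether few or many patients were affected.

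Moving plain KM to the whole SP does not cure this. In this population many patients die or stop for progression before any ocular-AESI-driven change. Treating those exits as ordinary censoring inflates the estimated probability.

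**Working it through.** The protocol gives no figure for this analysis, so there is none to reproduce.

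**1. Which patients the KM item covers**
- For the restricted reading: the KM item repeats the three event types of the lead-in, and the duration item comes after it. Section 3.9 puts that duration item inside the ocular-AESI item. The list therefore seems to run at least as far as the duration item, with the KM item in between.
- Against it: the section is headed for the SP. The proportion under the same lead-in would be 100% if the lead-in fixed the denominator. In the text as extracted, the KM item stands at the outer bullet level. That indentation is weak evidence: it follows a page break, and 3.9 prints flat some items that 8.7.2.3 prints nested.

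The restricted reading is the more natural one, but it is not certain.

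**2. Inputs**
- N = 150 and T = 15 months of follow-up (3.8, section 5).
- 3% ocular-related permanent discontinuation and median PFS of 2.8 months (6.1). The PFS median is used as a proxy for leaving treatment.
- 30% affected and constant hazards are assumptions. The documents give no rate for ocular dose reductions or delays.

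**3. Affected patients only**

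For the composite, every patient in the set has the event, so nothing is censored and KM is the ordinary sample median. At 3%, 150 × 0.03 = 4.5 patients.

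(a) No competing exit. With p affected by month 15, λ = −ln(1 − p)/15 and the median among affected is −ln(1 − p/2)/λ.
- p = 0.03: λ = 0.00203; median = 0.01511/0.00203 = 7.4 months.
- p = 0.30: λ = 0.02378; median = 0.16252/0.02378 = 6.8 months.

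(b) Competing exit fixed at μ = ln 2/2.8 = 0.2476 per month. Choose λ so that [λ/(λ + μ)] × [1 − exp(−15(λ + μ))] = p. With h = λ + μ and F = 1 − exp(−15h), the median among affected is −ln(1 − F/2)/h.
- p = 0.03: λ = 0.0078; median 2.6 months.
- p = 0.30: λ = 0.1068; median 1.9 months.

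(c) Total hazard fixed at 0.2476, with only the ocular share varying: the median is 2.8 months at any share (2.7 if truncated at month 15).

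A tenfold difference in risk moves the median by 0.6 to 0.7 month, or not at all.

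**4. Whole SP, plain KM, other exits censored**

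Total hazard 0.2476 and ocular share s, so 0.2476 × 15 = 3.713.
- Cumulative incidence at 15 months = s × (1 − exp(−3.713)) = 0.976s.
- 1 − KM at 15 months = 1 − exp(−3.713s).

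| s | Cumulative incidence | 1 − KM |
|---|---|---|
| 0.03 | 2.9% | 10.5% |
| 0.30 | 29% | 67% |

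Under model (b), 1 − KM is about 11% and 80%, against 3% and 30%.

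The KM median misleads too. At s = 0.30 it would be 2.8/0.30 = 9.3 months, although fewer than a third of patients ever have the event.

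**The case against.** The strongest reply is that the restriction is inferred from a broken list. The section is headed for the SP, the lead-in also governs a proportion that needs the SP as denominator, and the KM item does not name a cause. If it means discontinuation for any cause, as 3.9 seems to, stopping for progression is an event and that source of bias disappears. This stands in part: the text is ambiguous. But on the any-cause reading, the ocular-impact objective has no time-to-event analysis. Both ocular-cause readings give a poor estimate.

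A second reply is that competing-risk handling belongs in the SAP. The SAP could settle the censoring rule, but the protocol itself names the estimator and writes the selecting lead-in.

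Three stronger readings are tempting, and the documents do not support them.
- A reader might infer that the risk is never reported. It is: the number and proportion affected are planned in 3.9 and 8.7.2.4.
- A reader might infer that every KM curve here must fall to zero. That holds for the composite. For one component, such as discontinuation, patients who had only another type of change remain without the event.
- A reader might treat discontinuation as competing with the first ocular AESI as well. Sections 8.1 and 8.3.5 collect ocular AESIs after treatment stops, so that rule would discard first events the study intends to record.

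**Conclusion.** The point holds in a limited form. On its most natural reading, the KM item conditions on the event it is meant to time, and its median is nearly insensitive to how many patients are affected. For ocular discontinuation at the cited 3%, it would rest on 4 to 5 of 150 patients. Crude risk is still reported, so the loss is in the timing estimate, which does not describe the impact of ocular AESIs on treatment.

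The overstatement by whole-SP KM (10.5% against 2.9%, 67% against 29%) illustrates why changing the population alone is not enough. It rests on constant hazards and on median PFS standing in for time to leaving treatment. The 3% concerns permanent discontinuation only, and the 30% is assumed. The protocol does not state that whole-SP analysis, so these figures are not errors in a planned result. The primary objective is unaffected.

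**What to change.** Reword the KM item in 8.7.2.4, and carry the detail into the SAP:
- Risk set: all SP patients. Origin: first dose. Event: first dose reduction, interruption/delay or discontinuation due to an ocular AESI, for each type and for the composite.
- Estimate: Aalen-Johansen cumulative incidence with 95% CI at 3, 6, 12 and 15 months, the times already used for persistence. Competing events: death, and permanent discontinuation for other reasons or a new line of treatment.
- Onset times among affected patients: simple summaries labelled descriptive, not KM.
- Time to discontinuation for any cause: may stay as KM.
- Time to first (specific) ocular AESI over full follow-up: only death competes. Discontinuation competes only in an analysis explicitly limited to the on-treatment or active-exposure window.

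The cost is minor wording and programming. Tables 3, 5 and 6 already plan the data. Table 3 codes the reason only as any AE, so ocular attribution has to come from the action taken in Table 5. Some medians will be not reached, which is the honest result where fewer than half the patients are affected.

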As shown in [Figure 1](#), eligible RRMM patients from sites who received their first belantamab mafodotin dose before study enrolment will only be invited for study participation if this is deemed necessary based on the enrolment rate in the EU.

Belantamab mafodotin use and ophthalmic monitoring data will be collected while patients are on treatment. Safety and effectiveness data will be collected regardless of whether patients are on treatment or have discontinued treatment during follow-up.

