8.2.3. EU Setting Considerations

8.3. Variables

8.3.1. Definitions

[figure not shown]
The following definitions apply to the different timings of data collection (see [Figure 2](#)):

- **Index date** is defined as the time of the first (non-missing) dose of belantamab mafodotin.
- **The baseline period** for data collection is defined as the time from the initial MM diagnosis until the index date (the first dose of belantamab mafodotin).
- **The post-index period** spans from the index date until the end of follow-up at 15 months, study discontinuation for any reason, informed consent withdrawal or death; whichever comes first.
- **The post-index treatment period** is defined as the duration of the belantamab mafodotin line of treatment (DoT). This spans from the index date until the confirmed decision date of permanent discontinuation of belantamab mafodotin treatment, the

confirmed date of a new line of treatment or the date of the end of follow-up at 15 months, study discontinuation for any reason, informed consent withdrawal or death; whichever comes first.

- **The study period** spans from the time from the initial MM diagnosis until the end of follow-up at 15 months, study discontinuation for any reason, informed consent withdrawal or death; whichever comes first.
- **Active treatment exposure periods** are defined as the time that belantamab mafodotin is considered to have a treatment effect during the post-index treatment period. This period includes all doses occurring within 70 days of the previous dose (belantamab mafodotin's half-life) from the date of the first belantamab mafodotin dose of that sequence to the date of the last dose +70 days or the date of the end of the post-index treatment period; whichever comes first.

Figure 2 Timings of Data Collection

[figure not shown]
Abbreviations: MM=multiple myeloma.

The following definitions apply to collection of treatment data:

- **Line of treatment** is defined as one or more completed cycles of a single agent, a regimen consisting of a combination of several drugs, or a planned sequential therapy of various regimens (Rajkumar, 2015).
- **A treatment cycle** is defined as the belantamab mafodotin label-approved dosing interval, which is 21 days (with a real-world scheduling grace period of +7 days).
- **Treatment discontinuation** is defined as a recorded clinician decision (with an associated decision date) to permanently discontinue belantamab mafodotin treatment.

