- **Treatment interruption** is defined as withholding ≥ 1 belantamab mafodotin dose for any reason without a confirmed clinician decision to permanently discontinue treatment or initiate a new line of treatment. The time interval between doses will be >2 treatment cycles (+ 7-day grace periods).
- **Treatment delay** is defined as a delay (intentionally or unintentionally) in receiving belantamab mafodotin without skipping a dose. The time interval between doses will be >1 treatment cycle (+ a 7-day grace period) and <2 treatment cycles.

Figure 3 shows examples of treatment sequences that patients might undergo during the 15-month follow-up period.

Figure 3 Examples of treatment sequences during the post-index period

The following definitions apply to derived outcomes for statistical analyses:

- ORR is defined as the proportion of patients with a best response (sCR, CR, VGPR or partial response [PR]) during the study period evaluated by a responsible physician based on International Myeloma Working Group [IMWG] criteria if feasible or to local standard practice
- OS is defined as the time in months from the start of belantamab mafodotin treatment to the date of death due to any cause
- rwPFS is defined as the time in months from the start of belantamab mafodotin treatment to the date of the first documented disease progression or death, whichever occurs first
- DoR is defined as the time from the first documented evidence of PR or better until the earliest date of progressive disease (PD) or death among patients who achieved a response

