8.7.2.3. Analysis of Key Secondary Objectives

For the key secondary objectives, the following will be described for the SP (overall and by line of treatment) during active treatment exposure periods:

- Average cycle dose (sum of all doses divided by total number of administrations per patient)
- Frequency and timing of ophthalmic monitoring relative to belantamab mafodotin administration for each cycle (type(s), number of examinations; overall and according to monitoring before and after the occurrence of ocular AESIs as well as treatment dose and frequency)
- Ocular AESIs in RRMM patients exposed to belantamab mafodotin occurring during the study period:
 - Number, proportions, co-occurrence and time to (specific) ocular AESIs; overall and by System Organ Class (SOC) and Preferred Term (PT) terms (MedDRA classification) and according to severity, grade, seriousness, action taken, duration, impact on daily living and relationship to treatment as well as treatment dose and frequency
 - Number, proportion, severity, grade, seriousness and duration of ocular AESIs by ophthalmic monitoring frequency, type(s) and timing relative to administration
 - Severity, grade, seriousness and duration of ocular AESIs by their treatment impact (e.g., dose changes, duration of interruptions/delays, discontinuation), use of artificial tears and dry eye comorbidity

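### Adherence is defined as time on treatment over total follow-up, so it tracks permanent discontinuation and later survival, not whether scheduled doses were given

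*Protocol*

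**What the plan says.** Evaluating persistence and adherence is one of the other secondary objectives (Protocol Sections 3.3 and 7.2). Section 8.7.2.4 gives the formula: "Belantamab mafodotin treatment adherence, i.e., the total duration of treatment in days divided by the total follow-up time in days". The same section defines persistence separately, as the proportion still on treatment at 3, 6, 12 and 15 months, and also plans a Kaplan-Meier summary of duration of treatment (DoT).

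Both parts of the ratio follow from Section 8.3.1:

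- **Numerator.** The post-index treatment period is equated with DoT: "This spans from the index date until the confirmed decision date of permanent discontinuation of belantamab mafodotin treatment", or until a new line of treatment or the end of follow-up if earlier. Nothing is subtracted for interruptions. An interruption "is defined as withholding ≥ 1 belantamab mafodotin dose for any reason without a confirmed clinician decision to permanently discontinue treatment", so held time lies inside the period.
- **Denominator.** Follow-up is the whole window after the first dose; it "spans from the index date until the end of follow-up at 15 months, study discontinuation for any reason, informed consent withdrawal or death". Section 8.1 adds: "Safety and effectiveness data will be collected regardless of whether patients are on treatment or have discontinued treatment during follow-up". Follow-up therefore continues after treatment stops.

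A treatment cycle "is defined as the belantamab mafodotin label-approved dosing interval, which is 21 days", with a 7-day grace period. Section 8.7.2.3 has a related summary: "Average cycle dose (sum of all doses divided by total number of administrations per patient").

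**The concern.** Adherence should say how closely dosing followed the schedule while the patient was meant to be treated. This ratio compares two calendar spans, and neither depends on how many doses were given. It can therefore fail in both directions: a fully dosed patient can score low, and a patient with many withheld doses can score 100%.

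The risk is misreading. A reported adherence of around 40% would look like poor compliance even if no dose had been missed. A comparison between subgroups could reflect how long patients lived after stopping. This is a stated formula, not a detail left open, so an analysis plan that follows it inherits the problem.

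**Working it through.** The protocol gives no expected adherence figure, so there is none to reproduce. The formula is applied as written.

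**Worked patients.** Inputs: 21-day cycle and 15-month cap (Section 8.3.1), with 15 months = 15 × 30.4375 = 456.6 days and 3 months = 91.3 days. Scheduled doses fall on days 0, 21, 42 and so on: 5 within 91.3 days and 22 within 456.6 days.

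| Patient | Treatment days / follow-up days | Ratio as defined | Doses given / scheduled |
|---|---|---|---|
| A: every dose, stops at 3 months, followed to 15 months | 91.3 / 456.6 | 20% | 5/5 = 100% |
| B: same dosing, dies on treatment at 3 months | 91.3 / 91.3 | 100% | 5/5 = 100% |
| C: dosed every 42 days for 15 months | 456.6 / 456.6 | 100% | 11/22 = 50% |
| D: dosed every 63 days for 15 months | 456.6 / 456.6 | 100% | 8/22 = 36% |
| E: dosed every 21 days for 15 months | 456.6 / 456.6 | 100% | 22/22 = 100% |

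A and B have identical dosing and score 20% and 100%. C, D and E differ up to 2.75-fold in doses given (22/8) and all score 100%.

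**Alternative numerator.** Section 8.7.2.4 does not say that total duration of treatment means DoT. Suppose it means the active treatment exposure periods of Section 8.3.1, which bridge gaps of up to 70 days. A and B are unchanged, because those periods are capped at the end of the treatment period. C and D still score 100%. Dosing every 84 days gives (5 × 70 + 36.6)/456.6 = 85%, against 6/22 = 27% of scheduled doses.

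**Population size of the effect, with no missed dose.** The ratio is min(DoT, OS, 15)/min(OS, 15), simulated with 400,000 patients and independent exponential times. The median OS of 13.7 months and median PFS of 2.8 months, used as a proxy for treatment duration, are the pivotal-study figures in Section 6.1. The OS median of 8.5 months is the midpoint of the 7 to 10 months given there. The 6-month treatment median is my assumption.

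- Treatment median 2.8, OS median 13.7: mean 42%, median 30%, and 66% of patients below 50%.
- Treatment medians 2.8 to 6 with OS medians 8.5 to 13.7: mean about 42% to 66%.

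PFS already includes death, so taking the minimum with an independent OS shortens the effective median treatment time to 2.33 months. A second model avoids this: treatment stops at the PFS event, 10% of those events are deaths (assumed), and survival after progression is set to give the required OS median. With PFS 2.8 and OS 13.7 months the mean is again 42%. Changing only the OS median gives 49% at 8.5 months and 37% at 27.4 months. Longer survival alone lowers the ratio.

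**Average cycle dose.** The divisor is the number of administrations, so a cycle without an administration adds nothing above or below the line. Patients C, D and E, if given the full dose each time, all show 100% of it. Per scheduled cycle the values are 50%, 36% and 100%.

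**The case against.** The strongest reply is that withheld doses are covered elsewhere. The duration and reasons of interruptions, delays and dose modifications are a separate objective (Section 7.2). Interruption and delay are defined by dosing interval (Section 8.3.1). Every administration date and the prescribed and administered doses are collected (Table 3). Section 8.7.2.4 plans counts, timing and durations of changes due to ocular events of special interest, and Section 8.7.2.5 lists a subgroup of interrupted versus continuous treatment. Patient D's 63-day gaps exceed two cycles plus two grace periods (56 days), so that patient would be recorded as interrupted. All of this stands. A reader might infer that dose holding is invisible to the study, or that it is the main way ocular toxicity changes exposure. The documents contradict the first and give no basis for the second. What remains is that none of these data enter the adherence formula.

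A reader might also take the ratio to measure only progression and survival. That is too narrow: Table 3 lists adverse events, patient decision, end of treatment and other reasons for discontinuation, and each lowers it. It is a discontinuation measure in general.

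On average cycle dose, the formula stands beside the label, dose reductions do move it, and the protocol never offers it as adherence or dose intensity. That part is a labelling matter only.

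Finally, the simulations rest on assumed distributions. That is true, but the 20% versus 100% contrast needs none of them.

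**Conclusion.** The adherence definition is wrong as written. It yields the proportion of follow-up spent before permanent discontinuation or a new line of treatment, which DoT and persistence already describe, and it cannot answer the adherence part of the objective.

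Identical full dosing can score 20% or 100%, and half the scheduled doses can score 100%. The first result holds whether duration of treatment is read as DoT or as active exposure periods. The second holds fully under DoT, and for gaps of up to 70 days under the other reading. The population figure of about 42% to 66% with perfect dosing is illustrative. It depends on exponential times, on PFS standing in for treatment duration, and on a treatment median of up to 6 months that the protocol does not state.

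The measure is a descriptive item among the other secondary objectives. No hypothesis is tested, the study size does not depend on it, the primary objective is baseline characterisation, and no collected data are lost. The formula should be fixed before analysis, but it does not put the study's main results in doubt.

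**What to change.** 1. Compute adherence within the post-index treatment period only, as administrations received divided by administrations scheduled from the index date to the end of that period.
2. State one counting rule, because a bare 21-day count is not neutral: dosing every 28 days is within the grace period, yet would score 17/22 = 77%. One workable rule treats intervals of up to 28 days (21 + 7) as on schedule. A longer interval of g days between doses adds floor(g/21) − 1 missed administrations. If the interval from the last dose to the end of the period exceeds 28 days, it adds floor(g/21). Under this rule 28-day dosing scores 17/17 = 100%, a 35-day delay adds no missed dose, patient C scores 11/(11 + 10 + 1) = 50% and patient D scores 8/(8 + 14) = 36%.
3. Report adherence with and without clinician-directed holds counted as missed. Table 3 records the reason for interruption or delay as any adverse event, patient decision or other, so the plan should state which of these count as clinician-directed.
4. Rename the present ratio 'proportion of follow-up on treatment', and say whether its numerator is DoT or the active exposure periods.
5. Relabel average cycle dose as 'mean dose per administration'. A dose per scheduled cycle can be added if wanted.

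Cost: two definitions reworded and slightly more programming. Administration dates and prescribed and administered doses are already collected, so no new data are needed.
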